4.4 Sample size calculation

TB31F is a first in human observational safety trial in healthy volunteers, designed to identify safety concerns associated with TB31F administration at different dosages. A total of twenty-five healthy adults (males and females) aged 18 – 35 will be divided over five groups. Each group will include five subjects. The study's original sample size of n=20 (four intravenous groups of n=5), was calculated to have a 90% chance of observing at least 1 event if the true rate of such an event is 10.87% or more; and there is a 90% chance of observing no events if the true rate is 0.52% or less. The 5th (subcutaneous) was subsequently pragmatically chosen to have the same size. Sample size for each group is appropriate for mAb administration Phase 1 trials based on similar trial designs for HIV, CMV, and anthrax monoclonal antibody prophylactic studies [13-15]. This is a small Phase 1 study; therefore, it is largely descriptive and is intended to provide primarily safety data of 4 escalating intravenous doses of mAb TB31F and one subcutaneous dose of mAb TB31F. Comparative statistics will be performed but will have low power to detect anything other than very large differences between the groups. 5 reserve subjects will be recruited (1 reserve subject per group).

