8.2 Randomization, blinding and treatment allocation

This will be an open-label trial to enable appropriate safety evaluation prior to proceeding to the next dose group. Randomization will not be used in this study. Subjects may choose in which of the five groups they wish to be enrolled. The time of notification and treatment group will be documented in the electronic case report form (eCRF).

If the enrollment criteria are met, the eligible subjects will be entered in the study. Screening applicants will receive a screening number of two letters and a corresponding volunteer number as soon as they return their application form. Study numbers will not represent or include any private identifiable information.

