If a subject withdrawal occurs for any reason, the investigator must make every effort to determine the primary reason for a subject's withdrawal from the study and record this information in the study file. However, in accordance with the principles of the current version of the Declaration of Helsinki, a subject does have the right to withdraw from the study at any time and for any reason and is not obliged to give his or her reasons for doing so.

With permission of the subject, all data generated before withdrawal will be included in final study analysis with subject's permission, unless it is felt that the data is compromised. Blood samples collected before withdrawal will be used/stored unless the subject specifically requests otherwise.

As a result of occurrence of an adverse event/serious adverse event

If any subject develops an AE/SAE leading to premature withdrawal, the event will be fully followed-up. For premature withdrawal in connection with the emergence of an AE/SAE that is considered to be clinically relatively favorable (for example, the diagnosis is known, and it is expected to be resolved completely within a week), intermittent follow-up may be accepted as long as the plan for follow-up of the event is fully described in the notes section of the subject's CRF. Follow-up visits will be carried out for all subjects who are withdrawn due to occurrence of an AE or in connection with a change in any other safety indicator (vital sign or clinical laboratory result).

All data generated before withdrawal will be included in final study analysis with subject's permission, unless it is felt that the data is compromised. Blood samples collected before withdrawal will be used/stored unless the subject specifically requests otherwise.

As a result of lost to follow-up

To prevent lost to follow-up, subjects will be reminded by phone, email, or text message of their next study visit. In the event of a missed visit, subject will be contacted by phone within 1 day. A

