subject who misses two consecutive visits and cannot be reached or located after 5 attempts will be considered lost to follow-up. Efforts to contact the subject will be documented in source documents. Any subject who fails to attend the final study visit will also be classified as lost to follow-up. There will be no replacement for subjects who are lost to follow-up. All data generated before withdrawal will be included in final study analysis with subject's permission, unless it is felt that the data is compromised. Blood samples collected before withdrawal will be used/stored unless the subject specifically requests otherwise.

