10.1 Primary study parameter(s)

The number of subjects enrolled, completed, or withdrawn will be summarized. Reasons for withdrawal, when known, will be provided. Demographic data will be summarized by descriptive statistics and will include total number of observations (n), mean, standard deviation (SD) and range for continuous variables, and number and percentages for dichotomous variables. The primary safety, and reactogenicity outcomes will include all subjects who meet the eligibility criteria, receive study product mAb TB31F, and for whom safety data are available.

Safety Analyses

For the safety analysis, data from all subjects who received a dose of mAb TB31F and for whom safety data are available will be included. All analyses will be descriptive. Data will be presented by dose, overall/dose and overall/subject. Results will be summarized by study group. The percentage of subjects with at least one local AE (solicited and unsolicited), with at least one general AE (solicited and unsolicited) and with any AE during the solicited follow-up period will be tabulated with exact 95% CI (two-sided). No multiplicity adjustment will be implemented in analysis. The same calculations will be performed for AEs rated as grade 3. The percentage of subjects reporting each individual solicited local and general AE during the solicited follow-up period will be tabulated with exact 95% CI. The same tabulation will be performed for grade 3 AEs and for AEs with relationship to mAb TB31F administration. The reports of unsolicited AEs will be reviewed by a physician and will be categorized by ICD-10. The percentage of subjects with at least one report of unsolicited AE and reported up to 28 days after mAb TB31F administration will be tabulated with exact 95% CI. The same tabulation will be performed for grade 3 unsolicited AEs and for unsolicited AEs with a relationship to mAb TB31F administration. SAEs will be described in detail. Withdrawals due to AEs/SAEs will also be summarized. Vital signs which are outside of the normal range and clinically significant will also be listed in tables. The frequency of signs and symptoms will be compared between groups with the chi-square test or fishers exact test. Serious adverse events (SAEs) occurring at any point during the trial will be summarized and relatedness to vaccine will be assessed.

Clinical Laboratory Data Analyses

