10.5 Accounting for Missing, Unused, and Spurious Data

The SAP will be followed even if data are missing. For the safety analysis, data from all subjects who received a dose of mAb TB31F in the study will be included. Subjects with missing data will not be imputed. Subjects who miss an appointment date will not be removed from the study. Rather, their appointment and laboratory values will be recorded by appropriate missing value notation in the clinical database. Non-analyzable data will be documented in the deviations.

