## Analysis Methods

### Trial population

The primary safety and reactogenicity data will include all subjects who meet the eligibility criteria, receive study product mAb TB31F, and for whom safety, efficacy and immunogenicity data are available.

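### Protocol 8.4.2 lets a withdrawn subject's data be left out on an undefined judgement; for safety data this is inconsistent with the all-dosed rule in 10.1 and 10.5, and the SAP does not say which governs.

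*Protocol*

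**What the plan says.** **Withdrawal rule.** Protocol 8.4.2 deals in turn with several kinds of withdrawal. For an AE or SAE, and again for loss to follow-up, it says: "All data generated before withdrawal will be included in final study analysis with subject's permission, unless it is felt that the data is compromised". The paragraph on withdrawal of consent carries the same exception, "unless it is felt that the data is compromised". Neither document defines compromised data, says who decides, or says when.

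**Safety analysis rule.** Protocol 10.1 (Safety Analyses) says "data from all subjects who received a dose of mAb TB31F and for whom safety data are available will be included". For the safety analysis, Protocol 10.5 says "data from all subjects who received a dose of mAb TB31F in the study will be included". Neither sentence has an exception for compromised data.

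**SAP.** Under Adherence and protocol deviations, the SAP points to Protocol 10.5 for missing, unused and spurious data. Under Withdrawal and follow-up, it points to Protocol 8.4. It has no rule for compromised data and does not rank the two sections. Its Trial population paragraph restricts the safety set to eligible, dosed subjects "and for whom safety, efficacy and immunogenicity data are available".

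**Setting.** Protocol 8.2: "This will be an open-label trial to enable appropriate safety evaluation". Protocol 4.4: "Each group will include five subjects". Under Protocol 8.5, a subject cannot be replaced once dosed.

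**The concern.** The primary output is the percentage of subjects with AEs in each group, with an exact two-sided 95% CI (Protocol 10.1). That percentage depends on who is counted. For a dosed subject who then withdraws, 10.5 gives one answer and 8.4.2 allows another, depending on an unspecified person's view of the data.

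The clause covers all data and the final study analysis as a whole, so on its face it is not limited to laboratory samples. One of the three situations it covers is withdrawal because of an AE or SAE. Loss to follow-up is defined broadly: a subject who misses only the final visit falls under it, even with nearly complete safety data.

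With five subjects in a group, one inclusion decision moves the reported rate by a large step. Protocol 13.2 records no grade 3 AEs or SAEs in the first 20 subjects, and local solicited AEs in two of them. At such low counts a single subject can supply all the events of one type at a dose level.

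**Working it through.** **1. The sections side by side**

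| Place | Data covered | Who is in | Exception for compromised data |
|---|---|---|---|
| Protocol 8.4.2 (consent, AE/SAE, loss to follow-up) | All data before withdrawal, final analysis | Withdrawn subjects, with permission | Yes, undefined |
| Protocol 10.1, Safety Analyses | Safety | All dosed with safety data available | None |
| Protocol 10.5 | Safety | All dosed | None |
| SAP, Adherence and protocol deviations | Missing, unused, spurious data | Refers to 10.5 | None |

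The condition in 10.1 that data be available does not reconcile the sections, because data judged compromised still exist.

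**2. The plan's own figure.** Protocol 4.4 states, for the original 20 subjects, a "90% chance of observing at least 1 event if the true rate of such an event is 10.87% or more".

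- Rate giving a 90% chance of at least one event: 1 − 0.1^(1/20) = 10.87%, as stated.
- Rate giving a 90% chance of no event: 1 − 0.9^(1/20) = 0.525%, against 0.52% stated.

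Both reproduce, so no stated number is in dispute.

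**3. Losing one subject at random.** At a true rate of 10.87%:

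- n = 20: 1 − (1 − 0.1087)^20 = 90.0%
- n = 19: 1 − (1 − 0.1087)^19 = 88.8%

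The rate detectable with 90% probability at n = 19 is 1 − 0.1^(1/19) = 11.41%. This loss is small.

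**4. Losing the one subject who had the event.** This is an assumed case. The documents give no dropout rate and do not predict such an exclusion. Clopper-Pearson 95% limits:

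- 1/5, lower: 1 − (1 − L)^5 = 0.025, so L = 1 − 0.975^(1/5) = 0.5%.
- 1/5, upper: (1 − U)^5 + 5U(1 − U)^4 = 0.025, so U = 71.6%.
- 0/4, upper: 1 − 0.025^(1/4) = 60.2%.
- 0/24, upper: 1 − 0.025^(1/24) = 14.2%.

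| | Subject counted | Subject excluded |
|---|---|---|
| Group | 1/5 = 20% (0.5% to 71.6%) | 0/4 = 0% (0% to 60.2%) |
| All subjects | 1/25 = 4.0% (0.1% to 20.4%) | 0/24 = 0% (0% to 14.2%) |

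The intervals overlap almost entirely. What changes is the point estimate, from one event to none. The problem is therefore selective exclusion, not lost precision.

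**The case against.** **Specific over general.** 8.4.2 is a general rule for all analyses, while 10.1 and 10.5 are specific to safety, and the SAP cites 10.5 for spurious data. One can read the exception as applying only to PK, SMFA and ADA data. This reading is reasonable, and it means a reader should not infer that the sections cannot possibly both hold. It does not close the gap. Nothing in either document says that 10.5 prevails, and the clause is restated for AE and SAE withdrawals without being limited to samples.

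**Not aimed at adverse events.** A reader might infer that the exception targets subjects who leave because of an event. It does not: the same words cover withdrawal of consent and loss to follow-up, and inclusion is the default in all three. The AE/SAE paragraph also requires full follow-up of the event.

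**Timing.** A reader might infer that exclusions would be decided with results in view. The documents do not say so. They say nothing on timing, and the trial is open label, so such a decision is not prevented. Protocol 10 has data verified before analysis, and 12.2 has queries resolved before database lock, but neither mentions this judgement.

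**Visibility of events.** This part of the objection largely stands. Protocol 10.1 describes SAEs in detail, summarises withdrawals due to AEs or SAEs, and lists all AEs by participant. Protocol 8.4.1 documents whether a reaction or AE led to withdrawal. Protocol 10.5 records non-analyzable data as deviations. Escalation and holding rest on SMC review of accruing data (9.5.3, 9.5.4), not on the final analysis. These provisions report an event, but they do not keep the subject in the numerator and denominator of the tabulated rate.

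**Constructed example.** The 1/5 to 0/4 case is a worst case and the analysis is descriptive. Both points are correct. The example shows what the wording permits, not what is expected.

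**Conclusion.** The point holds as an inconsistency that needs settling. 8.4.2 contains a discretionary exclusion rule with no criterion, decision maker or timing. For safety data it does not agree with 10.1 and 10.5, and the SAP leaves the order of precedence open.

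The size depends on an assumption: that one dosed subject with the only event in a group is excluded under the clause. The group rate then goes from 20% to 0%, and the overall rate from 4.0% to 0%. If the excluded subject is a random one, the effect is slight (90.0% to 88.8% at n = 20).

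The stronger inference, that a safety signal could vanish from the report or mislead dose escalation, is not supported. Narratives, withdrawal summaries, AE listings and SMC review should keep the event in view. What is exposed is the tabulated AE rates, their intervals and any group comparison built on them.

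The all-dosed principle is also broken elsewhere. The erroneous-inclusion paragraph of 8.4.2 excludes dosed but ineligible subjects, the first paragraph of 10.1 requires eligibility, and the SAP requires efficacy and immunogenicity data. Removing the clause alone would not secure the safety set.

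**What to change.** 1. **Protocol 8.4.2.** Delete the exception for safety data in all three paragraphs. State that all safety data of dosed subjects up to withdrawal are analysed under 10.5, consent permitting.
2. **Align the safety set.** Make the same all-dosed rule apply in the erroneous-inclusion paragraph of 8.4.2, the first paragraph of 10.1 and the SAP's Trial population paragraph. Eligibility and the availability of efficacy or immunogenicity data should not decide who is in the safety analysis.
3. **PK, SMFA and ADA data.** Allow exclusion only for documented sample or assay failure, under criteria fixed before database lock, such as assay validity criteria. Some failures show only in the readout, for example discordant ELISA duplicates or failed control feeders. The criteria should therefore be fixed in advance, without requiring each failure to be recorded before its result is seen.
4. **Reporting.** List every exclusion with its reason.

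The cost is protocol and SAP wording. Sample size, visits and assays do not change, and the subject's right to refuse use of data is kept.

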8.5 Replacement of individual subjects after withdrawal

If an assigned subject does not present on the day of mAb TB31F study product administration or elects to withdraw the consent on the day of study product administration, one of the reserve subjects will replace the subject. After subjects have received administration with mAb TB31F they cannot be replaced.

8.6 Follow-up of subjects withdrawn from treatment

A subject may end his or her participation in the study and still be followed up for safety, unless the subject chooses to have complete withdrawal of the consent for further participation in any trial procedures. If a subject chooses to withdraw from the study, the investigator will make a reasonable effort to determine the reason for the subject's withdrawal and complete the study termination eCRF.

8.7 Premature termination of the study

The study may be discontinued by the sponsor:

- On advice of the safety monitor
- On advice of the Safety Monitoring Committee (SMC)
- On advice of the clinical investigator
- On advice of the METC

The investigators, local safety monitor, SMC, METC or Sponsor may decide to put the study on hold based on adverse events, pending discussion with the Sponsor, SMC, METC, local safety monitor or investigators. Following discussion, it may be decided to terminate the study.

9. SAFETY ASSESSMENT AND REPORTING

9.1 Temporary halt for reasons of subject safety

In accordance to section 10, subsection 4, of the WMO, the sponsor will suspend the study if there is sufficient ground that continuation of the study will jeopardize subject health or safety. The sponsor will notify the METC without undue delay of a temporary halt including the reason for such an action. The investigator will take care that all subjects are kept informed. PATH REC will also be notified of any decision to prematurely suspend or terminate the study. Safety monitoring will be conducted throughout the study.

9.2 AEs, SAEs and SUSARs

9.2.1 Adverse events (AEs)

Adverse events are defined as any undesirable experience occurring to a subject during the study, whether or not considered related to the investigational product. All adverse events reported spontaneously by the subject or observed by the investigator or his staff will be recorded. Abnormal laboratory findings (e.g. clinical chemistry or hematology) or other abnormal assessments that are judged by the investigator to be clinically significant will be recorded as AEs (or SAEs if they meet the definition). The investigator will exercise his or her medical and scientific judgment in deciding whether an abnormal laboratory finding or any other abnormal assessment is clinically significant. If there are any severe complaints, the volunteer will be evaluated immediately by a qualified clinician using the appropriate clinical assessments according to standard hospital care.

9.2.2 Clinical Laboratory Parameters

To the extent possible, all normal ranges for clinical laboratory test results will be pre-specified in site reference range documents, but the investigator will exercise his/her medical and scientific judgment in deciding whether an abnormal laboratory finding or other abnormal assessment is clinically significant. Clinically significant abnormal laboratory findings that present at baseline and significantly worsen following the start of the study will also be reported as AEs or SAEs.

9.2.3 Serious adverse events (SAEs)

A serious adverse event is any untoward medical occurrence or effect that:

- results in death;
- is life threatening (at the time of the event);
- requires hospitalization or prolongation of existing inpatients' hospitalization;
- results in persistent or significant disability or incapacity;
- is a congenital anomaly or birth defect; or

- any other important medical event that did not result in any of the outcomes listed above due to medical or surgical intervention but could have been based upon appropriate judgment by the investigator.

An elective hospital admission will not be considered as a serious adverse event. The investigator will report all SAEs to the sponsor and the safety monitor without undue delay after obtaining knowledge of the events (within 24 hours). All SAEs will be reported through the web portal *ToetsingOnline* to the accredited METC that approved the protocol, within 7 days for SAEs that result in death or are life threatening followed by a period of maximum of 8 days to complete the initial preliminary report by the investigator/sponsor. All other SAEs will be reported within a period of maximum 15 days after the sponsor has first knowledge of the serious adverse event. Death is an outcome of an event. The event that resulted in the death should be recorded and reported on the SAE CRF.

9.2.4 Suspected unexpected serious adverse reactions (SUSARs)

Adverse reactions are all untoward and unintended responses to an investigational product related to any dose administered. Unexpected adverse reactions are SUSARs if the following three conditions are met:

1. the event must be serious (see chapter 9.2.3);
2. there must be a certain degree of probability that the event is a harmful and an undesirable reaction to the medicinal product under investigation, regardless of the administered dose;
3. the adverse reaction must be unexpected, that is to say, the nature and severity of the adverse reaction are not in agreement with the product information as recorded in:
 - Summary of Product Characteristics (SPC) for an authorized medicinal product;
 - Investigator's Brochure for an unauthorized medicinal product.

The sponsor will report expedited the following SUSARs through the web portal *ToetsingOnline* to the competent authority:

- SUSARs that have arisen in the clinical trial that was assessed by the METC.
- SUSARs that have arisen in other clinical trials of the same sponsor and with the same medicinal product, and that could have consequences for the safety of the subjects involved in the clinical trial that was assessed by the METC.

The remaining SUSARs are recorded in an overview list (line-listing) that will be submitted once every half year to the METC. This line-listing provides an overview of all SUSARs from the study medicine, accompanied by a brief report highlighting the main points of concern.

The expedited reporting of SUSARs through the web portal Eudravigilance or *ToetsingOnline* is sufficient as notification to the competent authority. The sponsor will report expedited all SUSARs

to the competent authorities in other Member States, according to the requirements of the Member States. The expedited reporting will occur not later than 15 days after the sponsor has first knowledge of the adverse reactions. For fatal or life threatening cases the term will be maximal 7 days for a preliminary report with another 8 days for completion of the report. As this is an open label study in which the sponsor, investigator and the SMC are not blinded, the code would not have to be broken in the case of a SUSAR.

